5.1.2 Additional study treatment

No additional treatment beyond investigational treatment is requested for this trial.

5.2 Treatment arms

There is one treatment arm in this open-label study.

5.3 Treatment assignment

Patients will not be randomized to treatment in this study; all patients previously treated with LCZ696 or enalapril in PARADIGM-HF will be treated with LCZ696 at maximally tolerated doses with a target dose of 200 mg bid.

An Interactive Response Technology (IRT) system will be used to enroll patients into the study and dispense study drug. The investigator or his/her delegate will contact the IRT after confirming that the patient fulfills all of the inclusion/exclusion criteria. The IRT system will prompt the investigator to enter the patient's Subject Number into the system and then assign a uniquely numbered medication kit for the first investigational treatment to be dispensed to the patient (at the time of successfully completing Visit 1).

The IRT will be used to assign additional uniquely numbered medication kits at Visits 2 through 8 of the trial.

5.4 Treatment blinding

Treatment is not blinded to either investigators or patients during the course of the study (i.e., it is "open-label"). All patients will receive LCZ696 at maximally tolerated doses with a target dose of 200 mg bid.

5.5 Treating the patient

5.5.1 Patient numbering

Each patient is uniquely identified by a Subject Identification (ID) Number. Patient will be assigned an ID number *similar* to that assigned in PARADIGM-HF at the time of Visit 1 (the exact identical number will not be used, due a change in the database system). More details for the patient ID number assignment are included in the eCRF completion guide (eCCG).

Upon signing the informed consent form, the investigator or his/her staff will contact the IRT and provide the requested identifying information (including the current subject ID and the original subject ID from PARADIGM-HF) to register the patient into the IRT system.

If the patient fails the first attempt to qualify for the study at Visit 1, the patient will have two (2) more opportunities to undergo screening with a minimum of 2 weeks between visits, as indicated in Section 6.1 of this protocol. IRT must be contacted at each screening attempt.

If the patient fails to be treated for any reason, the IRT must be notified within 2 days that the patient was not treated. The reason for not being treated will be entered on the Screening Disposition CRF.

5.5.2 Dispensing the investigational treatment

Each study site will be supplied by the Sponsor with investigational treatment in packaging of identical appearance.

The investigational treatment packaging has a 2-part label that includes the medication kit number. The site staff will identify the investigational treatment package(s) to dispense to the

patient by contacting the IRT and obtaining the medication number(s). Immediately before dispensing the package(s) to the patient, the site staff will detach the outer part of the label from the packaging and affix it to the source document (Drug Label Form) for that patient's unique Subject Number.

5.5.3 Handling of study treatment

5.5.3.1 Handling of investigational treatment

Investigational treatment must be received by a designated person at the study site, handled and stored safely and properly, and kept in a secured location to which only the investigator and designees have access. Upon receipt, all investigational treatment should be stored according to the instructions specified on the labels. Clinical supplies are to be dispensed only in accordance with the protocol. Technical complaints are to be reported to the respective Sponsor's Quality Assurance.

Medication labels will be in the local language and comply with the legal requirements of each country. They will include storage conditions for the investigational treatment but no information about the patient except for the medication number. This study will be conducted as an open-label study, with no treatment blinding.

The investigator must maintain an accurate record of the shipment and dispensing of investigational treatment in a Drug Accountability Log. Monitoring of drug accountability will be performed by the field monitor during site visits and at completion of the trial. Patients will be asked to return all unused investigational treatment and packaging at the end of the study or at the time of discontinuation of investigational treatment.

At the conclusion of the study, and as appropriate during the course of the study, the investigator will return all unused investigational treatment, packaging, drug labels, and a copy of the completed Drug Accountability Log to the Sponsor's monitor or to the Sponsor's address provided in the investigator folder at each site.

5.5.3.2 Handling of other study treatment

Not applicable

5.5.4 Instructions for prescribing and taking study treatment

The Sponsor will supply the investigators with LCZ696 for the course of the study. Patients will be provided with bottles of medication sufficient to last until the next scheduled visit.

Open-label study medication will be dispensed at

Visit 1 upon fulfilling entry criteria,

Visit 2 (at 1 to-2 weeks after starting treatment with LCZ696),

Visit 3 (at 2-to-4 weeks),

Visit 4 (3 months),

Visit 5 (at 6 months),

Visit 6 (at 12 months),
Visit 9 (at 18 months),
Visit 8 (at 24 months) and longer if required.

LCZ696 will be supplied as film-coated tablets provided in the 50 or 100 or 200 mg strength.

All dosages prescribed and dispensed to the patient must be recorded in the IRT and on the Dosage Administration Record eCRF.

Visit 1

All patients must provide informed consent before any study-specific procedure is performed.

At Visit 1, patients' eligibility for enrollment will be assessed by the investigator. Laboratory values obtained within the last 5 days from visit 1 can be used to establish eligibility. If results from a recently drawn sample are not available, samples will be obtained during visit 1 to assess eligibility.

Patients not on current ACEI therapy: Patients will complete the tests required for visit 1 and, if fulfilling the entry criteria, they can be enrolled.

Patients on current ACEI therapy: Patients will complete the tests required for visit 1, and if fulfilling the entry criteria must complete a **36 h ACEI-free period** prior to beginning LCZ696 treatment.

Following completion of the study procedures for the visit 1, IRT will be contacted to enter the patient as screened. If the patient is eligible to enroll into the study, IRT will be contacted again to dispense LCZ696. The patient will start with 100 mg LCZ696 bid, unless the investigator decides that the patient should start with 50 mg bid. The patient will be instructed to take the bid p.o. dose for 1 to 2 weeks before returning to the study center for Visit 2.

The patients will be instructed to take their morning study drug p.o. dose at approximately 08:00 (8:00 AM) and their evening study drug p.o. dose at approximately 19:00 (7:00 PM). The study medication should be taken with a glass of water with or without food. If the patient misses taking any study drug dose, he/she should take it as soon as possible, unless it is almost time for the following scheduled dose. In this case, the patient should skip the missed dose and return back to his/her regular study drug administration schedule.

The investigator should promote compliance by instructing the patient to take the study drug exactly as prescribed and by stating that compliance is necessary for the patient's safety and the validity of the study. The patient should be instructed to contact the investigator if he/she is unable to take the study drug as prescribed for any reason.

Visit 2 (at 1-to-2 weeks after starting LCZ696 treatment)

Study procedures will be completed, including an assessment of the patient's tolerability to LCZ696 50 mg bid (dose level 1) or LCZ696 100 mg bid (dose level 2).

IRT will be contacted and the patient dispensed bottles of LCZ696 for the target dose appropriate for each patient (depending on the dose-level tolerated in PARADIGM-HF and the judgment of the investigator). The recommended steps to up-titrate the dose are indicated below.

- For those who maximally tolerated **dose level 1** in PARADIGM-HF, additional tablets for a dose of LCZ696 50 mg bid will be dispensed at Visit 2 (if the investigator chooses not to administer a higher dose to the patient) and taken for 1-to-2 weeks before returning to the study center for Visit 3.
- For patients that maximally tolerated **dose level 2** in PARADIGM-HF, additional tablets for a dose of LCZ696 100 mg bid will be dispensed at Visit 2 (if the investigator chooses not to administer a higher dose to the patient) and taken for 1-to-2 weeks before returning to the study center for Visit 3.
 - However, if a patient tolerated dose level 3 in PARADIGM-HF, they will receive additional tablets for a dose of LCZ696 200 mg bid, which will be taken for 1-to-2 weeks before returning to the study center for Visit 3.
- Any patient at dose level 1 or 2 can be up-titrated to a higher dose of LCZ696 at Visit 2 or any time thereafter at the discretion of the investigator.

LCZ696 tablets should be taken p.o. in the morning at approximately 08:00 (8:00 AM) and again in the evening at approximately 19:00 (7:00 PM). The instructions provided at Visit 1 for taking the tablets and compliance should again be reviewed with each patient.

Visit 3 (at 2-to-4 weeks), Visit 4 (at 3 months), Visit 5 (at 6 months), Visit 6 (at 12 months), Visit 7 (at 18 months) and Visit 8 (at 24 months)

Study procedures will be completed before contacting the IRT to dispensed bottles of LCZ696 50 mg, 100 mg or 200 mg tablets to patients. The instructions provided at Visits 1 and 2 for taking the tablets and compliance should again be reviewed with each patient.

Visit 9 (at 30 months)

Study procedures will be completed before contacting the IRT to record the patient's attendance for this visit but not to dispense study drug.

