5.1 Protocol requested treatment

5.1.1 Investigational treatment

All eligible patients will receive LCZ696 in addition to optimal CHF therapy, as considered appropriate by the investigator and in accordance with standard therapy guidelines, but with the exception of an ACEI or ARB as this will be replaced by LCZ696. The use of an ACEI or an ARB in addition to LCZ696 is strictly prohibited.

The Sponsor will provide the following open-label study medication in bottles:

- LCZ696 50 mg film-coated tablets (LCZ696 dose level 1)
- LCZ696 100 mg film-coated tablets (LCZ696 dose level 2)
- LCZ696 200 mg film-coated tablets (LCZ696 dose level 3)

Sufficient medication will be provided for treatment according to the study protocol, including additional medication to allow for delayed visits.

Medication labels will be in the local language and comply with the legal requirements of each country. They will include storage conditions for the drug.

The target p.o. dose of LCZ696 is 200 mg bid. For patients not tolerating the target dose, LCZ696 will be titrated down to a lower dose level twice a day, at the investigator's discretion, based on the defined safety and tolerability criteria ([Appendix 3](#), [Appendix 4](#) and [Appendix 5](#)).

For the initial treatment doses (50 or 100 mg bid) administered up to visit 2 and 3, the protocol indicates that the dose could be administered 1-to-2 weeks prior to the next visit. However, treatment should last for a **minimum of 1 week** before up-titrating to the next dose strength.

Recommended starting LCZ696 dose

For patients who tolerated **dose level 3** (either 200 mg LCZ696 bid or 10 mg enalapril bid) in the PARADIGM-HF study, the recommended starting dose is 100 mg LCZ696 bid. Similarly, for patients who maximally tolerated **dose level 2** (either 100 mg LCZ696 bid or 5 mg enalapril bid) in the PARADIGM-HF study, the recommended starting dose could be 100 mg LCZ696 bid. These patients can be up-titrated to 200 mg LCZ696 bid at a later time at the discretion of the investigator.

If, in the investigator's judgment, the patient may not tolerate the proposed starting dose of 100 mg LCZ696 bid, the patient could start with 50 mg LCZ696 bid and be up-titrated at the time of subsequent visits.

The starting dose of 50 mg bid is also recommended for patients who previously only tolerated dose level 1(either LCZ696 50 mg bid or enalapril 2.5 mg bid) in the PARADIGM-HF study.

Table 5-1 Recommended starting dose

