Dose levels used in CLCZ696B2314	Study treatment in CLCZ696B2314	Corresponding starting dose in this study LCZ696, mg bid
1	50 mg LCZ696bid or 2.5 mg enalapril bid	50
2	100 mg LCZ696bid or 5 mg enalapril bid	50 or 100
3	200 mg LCZ696bid or 10 mg enalapril bid	50 or 100

If the patient is taking an ACEI at the time of enrollment, a **36-hour washout** period is required before starting treatment with LCZ696.

If LCZ696 is *permanently* discontinued, treatment with an appropriate dose of an ACEI and/or ARB should be initiated. A 36-hour washout period is also required before starting treatment with an ACEI after discontinuation of LCZ696.

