If down-titration is necessary, the patient should be down-titrated to the next lower dose level (Table 5-2 below). The patient may continue to receive the lower dose level for a recommended period of 1 to 4 weeks, or longer based on the investigator's judgment, before re-challenging the patient with the next higher dose level. For example, a patient who encounters tolerability problems at the target dose of 200 mg LCZ696 bid (dose level 3), should receive the study drug at dose of 100 mg LCZ696 bid (dose level 2) for 1 to 4 weeks. Then, based on the investigator's judgment, he/she should be re-challenged with up-titration back to dose level 3.

Table 5-2 LCZ696 dispensed during the open-label treatment period

Study visit	Dose level	LCZ696
Dispensed at Visit 2 and all subsequent visits	3 ^a	200 mg bid
Dispensed at Visit 1 and available for any visit after Visit 1	2 ^b	100 mg bid
Dispensed at Visit 1 for patients that tolerated only dose level 1 in PARADIGM and available for any visit after Visit 1	1 ^c	50 mg bid

a. This dose level should be maintained for as long a duration as possible. If down-titration is necessary due to side effects, the patient should be re-challenged as soon as medically possible per the investigator's judgment.

b. Only if dose level 3 is not tolerated despite modification of other non-disease-modifying HF medications.

c. Only if dose levels 2 and 3 are not tolerated despite modification of other non-disease-modifying HF medications.

If the tolerability issues are not alleviated despite down-titration by one dose level, the investigator may lower the study drug dose further to the next lower level for 1 to 4 weeks, up to temporary or permanent withdrawal of the study drug. Again, once stable, the patient should be re-challenged with up-titration to the next higher dose level every 1 to 4 weeks in an attempt to bring back the patient gradually to the target study drug dose level (dose level 3).

The investigator may choose the next dose level for down- or up-titration according to his or her judgment (Table 5-2). As discussed in [Section 5.5.5](#), the IRT should be contacted to register any changes in the patient's LCZ696 dose level, including cases of temporary and permanent withdrawal of the study drug, and to obtain the medication numbers of the LCZ696 supplies required for the new dose level.

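### Two dosing passages conflict: Tables 5-1 and 5-2 disagree on who may start at 50 mg bid, and the Visit 2 step for dose-level-3 patients ignores the starting dose

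*Protocol*

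**What the plan says.** **Starting dose.** Protocol Section 5.1.1 recommends 100 mg bid for patients who tolerated dose level 3 in PARADIGM-HF, says 100 mg bid could be used for level 2, and recommends 50 mg bid for level 1. If the investigator doubts that 100 mg will be tolerated, "the patient could start with 50 mg LCZ696 bid and be up-titrated at the time of subsequent visits". Sections 3.1 and 5.5.4 (Visit 1) also leave a 50 mg start to the investigator. Table 5-1 puts this in rows:

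- Level 1: "50 mg LCZ696bid or 2.5 mg enalapril bid 50"
- Level 2: "100 mg LCZ696bid or 5 mg enalapril bid 50 or 100"
- Level 3: "200 mg LCZ696bid or 10 mg enalapril bid 50 or 100"

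**Dispensing table.** Table 5-2 in Section 5.5.5 describes 50 mg as "Dispensed at Visit 1 for patients that tolerated only dose level 1 in PARADIGM", and as available at any later visit. It lists 100 mg as dispensed at Visit 1 without restriction in the row label, and 200 mg from Visit 2. Footnote b, on 100 mg, reads "Only if dose level 3 is not tolerated despite modification of other non-disease-modifying HF medications". Footnote c, on 50 mg, is worded the same way for levels 2 and 3.

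**Visit 2.** Section 5.5.4 has patients return after 1 to 2 weeks on either 50 or 100 mg bid and assesses tolerability. It then gives steps by the level tolerated in PARADIGM-HF. For levels 1 and 2 the same dose is continued if the investigator chooses not to go higher. For level 3 the text is "if a patient tolerated dose level 3 in PARADIGM-HF, they will receive additional tablets for a dose of LCZ696 200 mg bid".

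**Pace of titration.** Section 5.1.1 requires at least 1 week on the initial dose "before up-titrating to the next dose strength".

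**The concern.** A level-3 patient may be started at 50 mg bid precisely because the investigator doubts that 100 mg will be tolerated. That start fits Table 5-1 but not the 50 mg row of Table 5-2. At Visit 2 the level-3 bullet then points the same patient to 200 mg bid without reference to the starting dose.

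Safety and tolerability is the only objective. Protocol Section 9.4 and SAP Section 9.7.1.6.1 list hypotension, hyperkalemia, renal dysfunction and AEs leading to dose adjustment, interruption or discontinuation among the primary safety items, and titration bears on all of them. SAP Sections 9.7.1.5.1 and 9.7.1.5.2 summarise duration on each dose level, time to first dose of each level, and patients per level by visit. If sites follow different passages, those summaries mix different titration rules. The same start could also be judged compliant under one table and a deviation under the other.

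**Working it through.** No sample size, power or event count is involved, and the plan states no figure to reproduce. The check sets the passages side by side.

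**Inputs.** Starts come from Table 5-1: one for level 1, two for level 2 and two for level 3, so 1 + 2 + 2 = 5 combinations. Permitted Visit 1 dispensing comes from the Table 5-2 row labels, and separately from footnotes b and c taken at face value. The Visit 2 dose comes from the bullets in Section 5.5.4, taking the dose named for each level. Dose levels 1, 2 and 3 are 50, 100 and 200 mg bid.

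| PARADIGM-HF level | Start, mg bid (Table 5-1) | Fits Table 5-2 row label | Fits footnotes read literally | Visit 2 dose, mg bid | Levels moved | Ratio |
|---|---|---|---|---|---|---|
| 1 | 50 | yes | yes | 50 | 0 | 1 |
| 2 | 50 | no | no | 100 | 1 | 100/50 = 2 |
| 2 | 100 | yes | yes | 100 | 0 | 1 |
| 3 | 50 | no | no | 200 | 2 | 200/50 = 4 |
| 3 | 100 | yes | no | 200 | 1 | 200/100 = 2 |

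**Table 5-1 against Table 5-2.** By row label, 3 of 5 starts agree and 2 of 5 do not: 50 mg for level 2 and 50 mg for level 3. With the footnotes read literally, 2 of 5 agree, because 100 mg for level 3 also fails footnote b.

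**Scope of the footnotes.** They stand under the adjustment part of Section 5.5.5, where the table is introduced for down-titration. Footnote b is attached to a row that itself lists 100 mg at Visit 1, before this study dispenses any 200 mg. That suggests later adjustment was meant. However, neither footnote says so or makes an exception for the first dose. The firm conflict is therefore the 50 mg row label; the footnotes add an ambiguity.

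**Visit 2.** Only 1 of 5 combinations, level 3 started at 50 mg, passes over a dose level. The same section expects some patients to arrive on 50 mg, so this combination is not excluded by design. Moving from 50 to 200 mg bid omits 100 mg, which is the next strength up.

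**Number affected.** This would need the count of level-2 and level-3 patients started at 50 mg bid. Neither document gives or projects it.

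**The case against.** The best case for the plan is investigator discretion. Section 5.5.4 introduces the Visit 2 bullets as recommendations, lets the dose depend on investigator judgment as well as the earlier level, and requires a tolerability assessment first. Its last bullet makes up-titration from level 1 or 2 discretionary. Section 3.1 allows patients to stay on 50 or 100 mg, and Section 5.5.5 lets the investigator choose the next level. Since 100 mg is the recommended start for level 3, the level-3 bullet plausibly describes only that path. The one-week sentence in Section 5.1.1 mainly sets a minimum duration and merely implies stepwise titration.

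Much of this stands. A reader might infer that the protocol orders a jump from 50 to 200 mg bid. It does not: a literal reading of one bullet leads there, and other text allows a different course. A reader might also infer that Table 5-2 rules out Table 5-1 as a whole, but three of the five starts agree with its row labels.

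Discretion does not remove the conflict, however. Section 5.5.5 ties the choice of next level to Table 5-2, and its restart paragraph refers to that table for the allowable level. The level-3 bullet alone omits the clause on investigator choice. Nothing in the discretion wording explains why 50 mg at Visit 1 is open to levels 2 and 3 in one table and confined to level 1 in the other.

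**Conclusion.** Two conflicts hold on the text. First, a 50 mg bid start for patients who tolerated level 2 or 3 is allowed by Table 5-1 and Sections 3.1, 5.1.1 and 5.5.4, but lies outside the 50 mg row of Table 5-2 (2 of 5 starts). The scope of footnotes b and c is unstated. Second, the level-3 bullet for Visit 2 is not conditioned on the starting dose. Read literally, it produces one two-level, four-fold step (1 of 5 combinations) after 1 to 2 weeks, which sits uneasily with the next-strength wording in Section 5.1.1. This rests on the text and tables alone, since Figure 3-1 is not visible.

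Two further inferences are not supported. Section 3.3 reports that over 90% of patients reached the target dose in the PARADIGM-HF run-in. A reader might conclude that most patients started at 50 mg here would be level-3 patients. That figure describes another phase, and those started at 50 mg are a selected group that includes the level-1 patients for whom 50 mg is recommended. A reader might also suppose that these passages determine which kits the IRT offers, but neither document describes its kit-selection rules.

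The study is single-arm and descriptive, so no error rate or sample size changes. Analysis-set membership is also unaffected, because SAP Table 9-1 has no dosing criterion beyond receipt of study drug. What is at stake is consistent dosing during titration, the classification of deviations, and the reading of the exposure and early safety summaries. That justifies a correction.

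**What to change.** The sponsor should reconcile Section 5.1.1 with Table 5-1, the Visit 1 and Visit 2 text in Section 5.5.4, and Section 5.5.5 with Table 5-2 and its footnotes, so that they state one consistent rule. Three questions need a single answer throughout:

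- who may start at 50 mg bid;
- what the Visit 2 step is for a level-3 patient who started at 50 mg bid;
- whether footnotes b and c cover starting doses or only later adjustment.

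The IRT set-up should then be checked against the reconciled text. Which dose or rule is right is a clinical decision for the sponsor, and none is proposed here. The cost is protocol wording, issued by amendment, and the IRT check. No analysis in the SAP needs to change.
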